4.6.4.5. Hypersensitivity, Anaphylactic and Infusion/Injection Related Reaction Followup

Data collected on Hypersensitivity, Anaphylactic and Infusion/Injection Related Reaction Followup CRF page will be listed. Information to be summarized includes the timing of the reaction relative to study drug administration, and characteristics of the injection site reaction: erythema, induration, pain, pruritis, and edema. Patient based and event-based summaries will be created.

Data collected on this page for gastrointestinal events will be summarized (See Section 4.6.4.4). Additionally, summaries will be created for mucocutaneous, cardiovascular, central nervous system, respiratory and general signs or symptoms in a similar way as for gastrointestinal events. Percentages will be calculated out of the number of participants in the Safety set.

4.6.4.6. Hepatic evaluation

Liver Biopsy Assessment, Hepatic Monitoring Procedures, Hepatic Risk Factor Assessment and Liver Related Signs and Symptoms data will be presented in listings.

• Hepatobiliary Disorders:

The AE database will be searched using Standardized MedDRA Queries (SMQs) to identify events consistent with hepatobiliary disorders. Detailed searching criteria can be found in Section 6.3 (Appendix 3). A summary by PT within SMQ will be provided.

• Acute Gallbladder Disease

The AE database will be searched using predefined SMQs to identify events consistent with acute gallbladder diseases. Detailed searching criteria can be found in Section 6.3 (Appendix 3). A summary by PT within SMQ will be provided.

• Liver Enzymes:

Analyses for laboratory analyte measurements are described in Section 4.6.4.1. This section describes additional analyses of liver enzymes. In addition, the following will be provided:

- A shift table of maximum to maximum alanine aminotransferase (ALT) measurement from baseline ($\leq 1 \times ULN$, > 1 × ULN) to postbaseline with the following categories $\leq 1 \times ULN$, >1 to <3 × ULN, ≥ 3 to <5 × ULN, ≥ 5 to <10 × ULN, $\geq 10 \times ULN$
- A shift table of maximum to maximum aspartate transaminase (AST) measurement from baseline ($\leq 1 \times ULN$, $> 1 \times ULN$) to postbaseline with the following categories $\leq 1 \times ULN$, >1 to $<3 \times ULN$, ≥ 3 to $<5 \times ULN$, ≥ 5 to $<10 \times ULN$, $\geq 10 \times ULN$.
- Shift tables of maximum to maximum total bilirubin and direct bilirubin from baseline to postbaseline with the following categories ≤1 × ULN, > 1 to <2 × ULN, ≥2 × ULN.
- Shift tables of serum alkaline phosphatase from baseline to postbaseline with the following categories $\leq 1 \times ULN$, >1 to $\leq 2 \times ULN$, $\geq 2 \times ULN$.

Of note, maximum baseline will be the maximum non-missing observation in the baseline period. The maximum postbaseline value will be the maximum non-missing

value from the postbaseline period. Planned and unplanned measurements will be included.

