Visit Interval Tolerance (Days)	+3/-7	0	±3	±3	±3		Flexibility is built into the screening visit to ensure adequate CGM session and appropriate timing for stopping the baseline GLP-1 RA and initiating tirzepatide at Visit 2; see Section 4.1.1.
Fasting Visit		Х			Х	Х	
Study intervention injection training with demo device		Х					Train participant with demo device prior to initial injection.
Review hypoglycemic events collected in the diary		Х	Х	Х	Х	Х	
Participant Diary							
Participant diary dispensed	Х	Х	Х	Х			Diary includes blood glucose values, collection of intervention administration, information on dosing date/time, and hypoglycemia. See Section 8.1.
Diary compliance check		Х	Х	Х	Х	Х	
Diary return		Х	Х	Х	Х	Х	
Laboratory Tests and Sample Collections							
Hematology	Х						
Hemoglobin A1C (HbA1c)	Х	Х	Х	Х	Х	Х	

GPIL	
l	
I8F-N	

Study 18F-MC-GP1L	Period I -   Screening	Period II -	Treatment	Period			Comments
Visit Number	1	2	3	4	5	ED	ED = carly discontinuation
Week Relative to Study Intervention Start	-3	0	4	8	12		
Visit Interval Tolerance (Days)	+3/-7	0	±3	士3	±3		Flexibility is built into the screening visit to ensure adequate CGM session and appropriate timing for stopping the baseline GLP-1 RA and initiating tirzepatide at Visit 2; see Section 4.1.1.
Fasting Visit		Х			Х	Х	
Clinical chemistry	Х	Х			Х	Х	Includes glucose testing.
Lipid panel		Х			Х	Х	
Urinalysis	Х						
Serum pregnancy	Х						Only for WOCBP and females with a history of tubal ligation. See Section 10.4.2.
Urine pregnancy (local)		Х			Х	Х	Collect for WOCBP only. The result must be available prior to first dose of intervention. Perform additional pregnancy tests if there is clinical suspicion of pregnancy, or as required by local law or regulation.
Follicle stimulating hormone (FSH)	X						Optional; perform as needed to confirm postmenopausal status. See Section 10.4.
Calcitonin	Х						

ЪЦ
Ģ
1Ċ
[8F-N

Study I8F-MC-GPIL	Period I - Screening	Period II -	Treatment	Period			Comments
Visit Number	1	2	3	4	5	ED	ED = early discontinuation
Week Relative to Study Intervention Start	-3	0	4	8	12		
Visit Interval Tolerance (Days)	+3/-7	0	±3	±3	±3		Flexibility is built into the screening visit to ensure adequate CGM session and appropriate timing for stopping the baseline GLP-1 RA and initiating tirzepatide at Visit 2; see Section 4.1.1.
Fasting Visit		Х			Х	Х	
Estimated glomerular filtration rate (eGFR)	Х						Calculate using CKD-EPI method.
Urinary albumin/creatinine ration (UACR)	Х						

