### **Period II: Treatment Period**

### Visit 2 Treatment Initiation

Participants arrive to the clinic in the fasting state. See Section 6.1 for intervention details.

This is the general flow for Visit 2:

- Participant returns screening CGM sensor for compliance review and data upload
- Study personnel confirm enrollment criteria
- Study personnel complete all required visit procedures, including the collection of vital signs, all baseline procedures, and sample collection, and
- Treatment initiation for eligible participants

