1.2. Study Design

SURPASS-SWITCH-2 is a study to assess the changes in glycemic control when switching from a stable dose of a GLP-1 RA directly to tirzepatide 5 mg in participants with T2D. It has the following main design attributes:

- Phase 4 study
- Multicenter, single arm
- Open label
- The study consists of 2 periods:
 - Screening period: 3 weeks, starting from Visit 1 to Visit 2.
 - Treatment period: 12 weeks, starting from Visit 2 to Visit 5, where Visit 2 (on Week 0) and Visit 5 (on Week 12) are fasting visits.
- No dose escalation will be employed during the trial. The goal is to initiate tirzepatide at 5 mg on Visit 2 (on Week 0) and maintain until Visit 5 (on Week 12).
- The study will enroll approximately 150 participants.

Treatment Initiation			End of Treatment
Continue Baseline GLP-1 RA	Tirzepatide	5 mg SC QW	
CGM Assessment	CGM Assessment	8	CGM Assessment 12
Period I: 3-week Screening	Period II: 1 Treatment	2-week period	>

2. Statistical Hypotheses

For the primary estimand with primary endpoint, mean change in HbA1c percentage from baseline to Week 12, the following hypothesis is planned to be tested for tirzepatide 5 mg. Let the mean treatment difference be defined as μ = mean of ([HbA1c percentage at Week 12] – [baseline HbA1c percentage]), the statistical hypotheses are formulated as follows:

H₀:
$$\mu \ge 0.0$$
 vs. H_a: $\mu < 0.0$

Operationally the hypothesis will be evaluated by 2-sided test, at a 2-sided alpha level of 0.05.

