4.1. General Considerations

Statistical analysis of this study will be the responsibility of Lilly or its designee.

Any change to the data analysis methods described in the protocol will require an amendment *only if* it changes a principal feature of the protocol. Any other change to the data analysis methods described in the protocol, and the justification for making the change, will be described in the statistical analysis plan or clinical study report. Additional exploratory analyses of the data will be conducted as deemed appropriate.

Nominal significance levels:

All tests of treatment effects will be conducted at a 2-sided alpha level of 0.05, unless otherwise stated, and all confidence intervals will be given at a 2-sided 95% level.

Timing of Primary Analysis:

Primary analysis will be performed at database release after Last Participant Last Visit (LPLV).

Definition of baseline:

Baseline is defined as the last non-missing measurement recorded on or before the date/time of first dose. If the measurement time is not specified, it is assumed that any measurement taken on the date of first dose occurred prior to dosing.

Populations for analysis:

- Analyses will use the EAS to evaluate the primary efficacy estimand for all (secondary and exploratory) endpoints.
- Safety analysis will be performed on the SS.

Pooling of data:

Study data will be pooled across centers.

Analysis Windows:

Visit windows will be defined for by-visit summary and analysis purposes. Summary data such as adverse events and concomitant medications which are not reported by visit will not use visit windows. Visit labels will be assigned to each post-baseline record based on the windows or intervals for study day relative to the date of first dose. A record with the study day closest to the target visit day (week \times 7 days + 1) will be chosen when multiple records fall in the same visit window. In case of a tie, the record with the earlier date will be chosen. If Day 1 is missing, the closest visit on or before the date of first dose will be used as baseline. All visits will be included in the summary tables for worst post-baseline values.

All efficacy and safety analyses will be based on the visit windows in Table 1.

Study Day Relative to First Dose	Visit	Target Day
Study day ≤ 1	Baseline	1
$2 \leq study \ day \leq 43$	Week 4 (Visit 3)	29
$44 \leq \text{study day} \leq 81$	Week 8 (Visit 4)	57
$82 \leq study \ day \leq 88$	Week 12 (Visit 5)	85

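### The maximum-to-maximum liver shift tables set two scheduled pre-dose draws against one post-dose draw, so they lean towards apparent improvement around 1× ULN

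*SAP*

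**What the plan says.** SAP 4.6.4.6 (Hepatic evaluation, Liver Enzymes) plans "A shift table of maximum to maximum alanine aminotransferase (ALT) measurement from baseline" to post-baseline, with matching tables for AST and for total and direct bilirubin. For ALT and AST the baseline side has two rows, at or below 1× ULN and above it. A note defines the two sides: "maximum baseline will be the maximum non-missing observation in the baseline period", and "The maximum postbaseline value will be the maximum non-missing" value from the post-baseline period. It adds: "Planned and unplanned measurements will be included". The alkaline phosphatase bullet does not say maximum to maximum, so it is unclear whether the note covers it.

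The general rule in SAP 4.1 differs: "Baseline is defined as the last non-missing measurement recorded on or before the date/time of first dose".

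In the Schedule of Activities (Protocol 1.3), the clinical chemistry row (comment: "Includes glucose testing") is marked at Visits 1, 2, 5 and ED only. Nothing is scheduled at Week 4 or Week 8. At Visit 2 the order is "Study personnel complete all required visit procedures, including the collection of vital signs, all baseline procedures, and sample collection, and" only then treatment initiation, so that sample is taken before the first dose. Protocol Appendix 2 places ALT, AST and both bilirubins in this panel.

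**The concern.** A maximum over two draws is higher on average than a single draw from the same distribution. Maximum-to-maximum tables suit trials with many post-baseline samples. Here the scheduled counts run the other way, two before and one after. More participants are placed in the above-ULN row at baseline than one sample would place there, and some of them fall back at Week 12 through within-person variation alone.

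In a randomised trial both arms would carry the same artefact, and a between-arm comparison would largely remove it. This trial has one arm, so the before/after shift is the whole comparison. An excess of downward shifts could be read as liver enzymes improving after the switch, and a modest upward drift could be offset.

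**Working it through.** **Inputs from the documents**
- Scheduled pre-dose draws: two (Visits 1 and 2). Scheduled post-dose draws: one (Visit 5, or ED for early leavers).
- Baseline period: not defined as a term. SAP 1.2 gives "Screening period: 3 weeks, starting from Visit 1 to Visit 2", and SAP 4.1 Table 1 labels every study day up to 1 as Baseline. If the period held only Visit 2, a maximum would normally have nothing to act on. Taking it to cover both visits is therefore an inference, though a reasonable one.
- Planned enrolment: approximately 150.
- The plan gives no figure for this effect, so there is none to reproduce.

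**Direction, without a model.** Take three exchangeable draws and no drug effect. Each is equally likely to be the largest, so the larger of the two pre-dose values exceeds the Week 12 value with probability 2/3, and the reverse holds with probability 1/3. One draw against one draw gives 1/2 each.

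**Shifts across ULN, no drug effect.** Let p be the share above ULN at any one draw, and d the share above ULN at one given draw but not at another. Then:
- last pre-dose value as baseline: up = d, down = d
- maximum of two: share above ULN at baseline = p + d
- maximum of two: down − up = (p + d) − p = d

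The spurious net improvement therefore equals d, the ordinary one-way rate of switching between two samples.

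**Size, under assumptions that are not in the documents.** Log-normal ALT, between-subject log SD 0.45, within-subject log SD 0.15–0.25, 15–30% above ULN, scheduled draws only:

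| p | Within SD | d (last value, each way) | Above ULN at baseline, p + d | Up (max rule) | Down (max rule) |
|---|---|---|---|---|---|
| 15% | 0.15 | 4.2% | 19.2% | 2.4% | 6.6% |
| 30% | 0.20 | 8.0% | 38.0% | 4.5% | 12.5% |
| 30% | 0.25 | 9.7% | 39.7% | 5.5% | 15.2% |

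In each row down − up equals d: 6.6 − 2.4 = 4.2, 12.5 − 4.5 = 8.0 and 15.2 − 5.5 = 9.7. There are about 2.8 downward shifts per upward shift (12.5/4.5). In 150 participants with all three draws, the net apparent improvement is 150 × 0.042 = 6.3 to 150 × 0.097 = 14.6 people.

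**A real 10% ALT rise** (p = 30%, within SD 0.20):
- maximum rule: about 38.0% above ULN before, 37.0% after; net 37.0 − 38.0 = −1.0 points
- last pre-dose value: 30.0% before, 37.0% after; net +7.0 points

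**Sensitivity to the assumptions.** With 10–30% above ULN, between-visit correlation 0.6–0.9 and total log SD 0.5, the counts per 150 are:
- no effect: 7.5–30.4 down and 2.8–11.4 up under the maximum rule, against 4.7–19.1 each way with Visit 2 as baseline
- 10% rise: net −8.8 to +1.1, against +5.6 to +10.5
- 20% rise: net +1.4 to +11.1, against +11.9 to +20.5

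A 10% rise can be cancelled or reversed in the table. A 20% rise stays visible but is understated.

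**The case against.** The strongest reply is that the plan already covers the gap. SAP 4.6.4.6 presents these tables as additions to 4.6.4.1, which summarises change from baseline, shifts between low, normal and high, and treatment-emergent high results for the same analytes. The general last-value baseline applies there, so a 10% rise should show. This largely stands. One doubt remains: 4.6.4.1 also takes the worst of several values within a visit, and Table 1 puts both pre-dose draws under Baseline, so which rule governs its baseline is not fully clear.

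A reader might infer that the tables could conceal serious liver injury. The documents do not support that. The baseline rule only decides which row a participant falls in. The post-baseline columns at ≥3×, ≥5× and ≥10× ULN for ALT and AST, and at ≥2× ULN for bilirubin, depend on the post-baseline value alone.

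A reader might also infer that the SAP contradicts its own baseline definition. Protocol 9.3.1 allows a different baseline where one is specified, and 4.6.4.6 specifies one. The objection is to how the choice fits this schedule.

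Nor do the lost upward shifts in the no-effect case represent true drug-related rises. They come from participants who were above ULN at Visit 1 and not at Visit 2, and declining to call these new elevations is a defensible, stricter reading.

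Unplanned post-baseline tests would offset some of the imbalance. However, the mandated repeat in Protocol 8.2.7 starts at ALT or AST ≥3× ULN (baseline below 1.5× ULN) or ≥2× baseline otherwise, so mild rises get no second draw under that rule. Unplanned repeats during screening would widen the imbalance.

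**Conclusion.** The concern holds in a limited form. The draw counts come straight from the documents. The direction of the artefact follows from them once the baseline period is read as Visits 1 and 2. The size rests wholly on assumed ALT variability and prevalence, and the calculation ignores the entry exclusion for ALT above 3× ULN and any unscheduled tests. On those assumptions the tables would show about 2.8 downward shifts per upward shift with no drug effect, and could cancel a uniform ALT rise of around 10%. The effect is confined to mild movement near 1× ULN and to baseline row assignment, in descriptive tables with no test or decision attached. It is worth correcting because a single-arm before/after display has no comparator to expose the artefact.

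**What to change.** In SAP 4.6.4.6, take the baseline side of the liver shift tables from the SAP 4.1 definition (last value before first dose), and set it against the maximum post-baseline value including unscheduled tests. Alternatively, keep the maximum-to-maximum tables and show this version beside them. Either way, define the baseline period, say whether alkaline phosphatase follows the same rule, and footnote the number of draws contributing to each side.

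The cost is a sentence or two in the SAP and one derivation change, with no new data. There are two modest downsides. Where unscheduled post-baseline tests occur, one baseline value against a maximum leans slightly towards showing rises. A participant above ULN only at Visit 1 may also count as a new elevation. Showing both versions makes these cases visible.

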4.6.4.7. Acute pancreatitis

Acute pancreatitis is an AE of special interest in all studies with tirzepatide, including this study.

AE listing of acute pancreatitis will be provided separately from other AEs. Determination of reported events will be through the pre-defined SMQ search for acute pancreatitis and MedDRA PT of pancreatitis chronic. Detailed searching criteria can be found in Section 6.3 (Appendix 3).

4.7. Other Analyses

4.7.1. Subgroup analyses

Subgroup analyses of the primary and secondary endpoint will be made to assess consistency of the improvement from baseline across subgroups.

The primary and secondary endpoints will be examined using the same MMRM model defined in Section 4.3.2. but additionally, a SUBGROUP term will be included as fixed effects. LS-means with their corresponding 95% CIs and P-values will be reported for the subgroups.

The following subgroups are defined:

- Age group: < 65 years vs ≥ 65 years
- Sex: female vs male
- Race: white vs black vs other
- Ethnicity: Hispanic vs not Hispanic
- Baseline GLP-1 RA: liraglutide vs semaglutide vs dulaglutide
- Baseline GLP-1 RA equivalent doses (adapted from Almandoz et al. 2020):
 - dulaglutide 0.75 mg and liraglutide 1.2 mg vs.
 - o dulaglutide 1.5 mg, semaglutide 0.5 mg, and liraglutide 1.8 mg vs.
 - dulaglutide 3 mg and semaglutide 1 mg vs.
 - dulaglutide 4.5 mg and semaglutide 2 mg
- Baseline HbA1c (<8.0%, >8.0%)

If the number of participants is too small (less than [10%]) within a subgroup, then the subgroup categories may be redefined prior to unblinding the study.

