#### 9.3.6. Subgroup Analyses

Subgroup analyses of the primary and secondary endpoint will be made to assess consistency of the improvement from baseline across the following subgroups

• Age group: < 65 years vs  $\ge 65$  years

- Sex: female vs male
- Race: white vs black vs other
- Ethnicity: Hispanic vs not Hispanic
- Baseline GLP-1 RA: liraglutide vs semaglutide vs dulaglutide
- Baseline GLP-1 RA equivalent doses (adapted from Almandoz et al. 2020):
  - dulaglutide 0.75 mg and liraglutide 1.2 mg vs
  - o dulaglutide 1.5 mg, semaglutide 0.5 mg, and liraglutide 1.8 mg vs
  - dulaglutide 3 mg and semaglutide 1 mg vs
  - o dulaglutide 4.5 mg and semaglutide 2 mg, and
- Baseline HbA1c (≤8.0%, >8.0%).

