4.3.2. Main analytical approach

The primary objective based on the efficacy estimand defined in Section 1.1 will be evaluated using the EAS dataset (Section 3). The primary analysis model for HbA1c measurements over time will be a mixed model for repeated measures (MMRM).

The observed changes in HbA1c level from baseline (Visit 2 on Week 0) to each of the scheduled post-baseline visits (Visit 3 on Week 4, Visit 4 on Week 8, and Visit 5 on Week 12) of each participant are the dependent variable. The baseline HbA1c value is incorporated as a covariate, and the visits are treated as fixed effects.

Mean change from baseline at Week 12 will be estimated by least square means (LS means), with accompanying P-value and 95% CI.

Operationally, the hypothesis defined in Section 2 will be tested at a two-sided 0.05 level by performing the test on the least square mean of changes from baseline at Week 12.

An unstructured covariance pattern will be used to estimate the variance-covariance of the withinparticipant repeated measures. Parameters will be estimated by REML with the Newton-Raphson algorithm and using the Kenward-Roger method for calculating the denominator degrees of freedom.

In case the model fails to converge, the following covariance structures will be tested in the following order:

- 1. Heterogenous Toeplitz
- 2. Heterogeneous First Order Autoregressive
- 3. Heterogeneous Compound Symmetry
- 4. Toeplitz
- 5. First Order Autoregressive, and
- 6. Compound Symmetry

The first covariance structure that converges will be used.

Missing data will not be imputed because the maximum likelihood estimate is unbiased for this model in case of a Missing at Random (MAR) mechanism. The P-value obtained for the least

square means for change from baseline will be used to determine the statistical significance to achieve the primary objective.

HbA1c values and change from baseline in HbA1c will also be summarized by visit using descriptive statistics.

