4.4.2. Main analytical approach

The same analytical approach will be applied for all secondary endpoints as for the primary endpoint, which is detailed under Section 4.3.2.

For secondary endpoints, MMRM will include baseline HbA1c ($\leq 8.0\%$, >8.0%) category as a covariate instead of continuous baseline HbA1c.

Objective	Efficacy Measure	Analysis Conducted	Additional information
CGM parameters	Change from baseline in %TAR at Week 12	MMRM as specified in Section 4.3.2.	 MMRM with terms for: Visits Baseline HbA1c category (≤8.0%, >8.0%) Baseline %TAR
CGM parameters	Change from baseline in TAR at Week 12	MMRM as specified in Section 4.3.2.	 MMRM with terms for: Visits Baseline HbA1c category (≤8.0%, >8.0%) Baseline TAR
FSG	Change from baseline at Week 12 in FSG	MMRM as specified in Section 4.3.2.	 MMRM with terms for: Visits Baseline HbA1c category (≤8.0%, >8.0%) Baseline FSG
Weight	Change from baseline at Week 12 in weight	MMRM as specified in Section 4.3.2.	 MMRM with terms for: Visits Baseline HbA1c category (≤8.0%, >8.0%) Baseline weight

Table 2.	Summary	of the	analysis	of Seconda	ry Endpoints.

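### For the baseline-HbA1c subgroup, SAP 4.7.1 adds SUBGROUP to models that already contain baseline HbA1c, so the planned LS means are either not estimable or a poor guide to consistency

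*SAP*

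**What the plan says.** The purpose is the same in both documents. Protocol 9.3.6 states: "Subgroup analyses of the primary and secondary endpoint will be made to assess consistency of the improvement from baseline across the following subgroups". SAP 4.7.1 repeats it, and baseline HbA1c split at 8.0% is one of seven factors listed.

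The method is one recipe for all seven. SAP 4.7.1 reuses the model of 4.3.2 for the primary and the secondary endpoints alike. The only change it makes for a subgroup factor is this: "additionally, a SUBGROUP term will be included as fixed effects". The output is fixed too: "LS-means with their corresponding 95% CIs and P-values will be reported for the subgroups".

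What the models already contain:
- HbA1c (SAP 4.3.2): "The baseline HbA1c value is incorporated as a covariate, and the visits are treated as fixed effects".
- Secondary endpoints (SAP 4.4.2): the HbA1c "category as a covariate instead of continuous baseline HbA1c". Table 2 lists that two-level category for %TAR, TAR, FSG and weight, and labels each model as the one in 4.3.2.

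On the baseline value, SAP 4.1 says: "Baseline is defined as the last non-missing measurement recorded on or before the date/time of first dose". SAP 4.3.2 identifies it as Visit 2. The protocol's Schedule of Activities also has an HbA1c at Visit 1, and inclusion criterion 3 shows that this one is a central-laboratory result.

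**The concern.** A subgroup table meant to show whether improvement is consistent should compare the average change in people at or below 8.0% with the average change in people above it. For six of the factors, adjusting for baseline HbA1c is ordinary covariate adjustment. For the seventh, the covariate is the variable that defines the groups. The model then either holds the same two-level factor twice, or it asks how the groups would differ if they had the same baseline HbA1c, which by construction they do not.

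At stake is one prespecified analysis. A reader could take two similar adjusted means as evidence that better- and worse-controlled switchers improve alike, when the adjustment itself removed the difference.

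SAP 4.7.1 also names no SUBGROUP-by-visit term. That is a separate matter, and adding the term would not cure this one.

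**Working it through.** **1. The plan's own figure.** Neither document gives a figure for the subgroup analysis. The stated power does reproduce: with N = 150, difference 0.3 and SD 1.1 (read as the SD of change), the standard error is 1.1/√150 = 0.0898 and 0.3/0.0898 = 3.34. Power is then 91.6% (normal) or 91.3% (noncentral t), against at least 90% stated. The planned effect of 0.3 is the yardstick below.

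**2. Secondary endpoints, read with 4.4.2 and Table 2.** The design columns are intercept (1), visits (3), HbA1c category (2), baseline value (1) and SUBGROUP (2), nine in all. The rank is 1 + 2 + 1 + 1 + 0 = 5, because SUBGROUP adds nothing. In every row the two category entries equal the two SUBGROUP entries, so any estimable combination must weight them equally. A SUBGROUP LS mean weights SUBGROUP (1, 0) and the category (0.5, 0.5), or the observed shares. These never match, so both LS means and their difference are not estimable. A numerical check agrees, with the category as a class or a numeric variable. With the duplicate dropped, the LS means are estimable.

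**3. HbA1c model.** Write the mean change at visit v as α_v + βb + γg, where b is baseline HbA1c and g = 1 above 8.0%.
- Difference in planned LS means, both at the overall mean of b: γ.
- Difference in actual subgroup means: β(mean b above − mean b at or below) + γ.

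The plan reports only γ. If change is linear in baseline, γ = 0 whatever the slope. With baseline assumed uniform on 6.5 to 9.0%, the group means are 7.25 and 8.50. A slope of -0.4 per 1% gives a true gap of -0.4 × 1.25 = -0.50, and a slope of -0.8 gives -1.00.

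**4. Simulation of the planned HbA1c model.** N = 150, three visits, SD 1.1, complete data, uniform baseline, 500 runs per scenario. Ranges cover an effect that grows over visits and one that is constant.

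| Assumed truth | True gap | Mean LS-mean gap |
|---|---|---|
| Linear, -0.4 per 1% | -0.50 | -0.01 to -0.02 |
| Linear, -0.8 per 1% | -1.00 | 0.00 to -0.03 |
| Step of -0.5 at 8.0% | -0.50 | -0.38 to -0.50 |
| Flat to 8.0%, then -0.8 per 1% | -0.40 | -0.11 to -0.17 |
| -0.8 per 1% to 8.0%, then flat | -0.60 | +0.12 to +0.18 |

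The standard error of the LS-mean gap is about 0.31. A truncated-normal baseline (mean 7.4, SD 0.7) gives the same pattern.

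**5. Allowing for measurement error.** Assumed: true HbA1c mean 7.5%, between-person SD 0.8, within-person SD 0.3, Visit 1 limited to 6.5–9.0%. The overall mean baseline is then about 7.6%.
- Change of -0.30 at 7.5% with slope -0.4: true -0.23 and -0.61; planned LS means -0.35 and -0.32.
- Step from -0.05 to -0.80 at 8.0%: true -0.10 and -0.63; planned LS means -0.17 and -0.46.

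**6. What happens if the covariate is simply removed.** With a true change of -0.30 in everyone, grouping on Visit 2 gives -0.24 and -0.45. That is a spurious gap of 0.21 (0.10 to 0.34 for within-person SD 0.2 to 0.4). Grouping on Visit 1 gives -0.30 and -0.30 if the two visits' errors are independent. It gives -0.29 and -0.35 at error correlation 0.5, and -0.28 and -0.39 at 0.8.

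**The case against.** **Literal reading.** SAP 4.7.1 points to 4.3.2, whose covariate is continuous baseline HbA1c, so the secondary LS means can be estimated. This stands as a reading. A reader might infer that the secondary analysis fails outright on any reading, and the documents do not support that. The literal reading does, however, bring in the common-baseline problem of step 3. If the category is kept instead, the failure would be visible in the output and a programmer would probably drop a term. The SAP does not say which, and the table specifications are in a separate document.

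**The covariate has a benefit.** With a uniform change of -0.30 the planned model gives about -0.31 and -0.27, so it largely avoids the spurious gap in step 6. This stands. Regression to the mean is not a fault of the plan as written. It is a cost of the obvious repair. The choice between adjusted and unadjusted subgroup means is partly a choice of what to estimate, but the stated aim is consistency of improvement from baseline, and the adjusted contrast does not describe that.

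**Low stakes.** Protocol 6.3 calls the study descriptive, SAP 2.1 makes no multiplicity adjustment, and no objective asks about this subgroup. That limits the importance and leaves the defect in place.

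**Cut-point.** SAP 4.7.1 prints a strict less-than sign at 8.0%, which would leave exactly 8.0% in neither group. Other SAP sections and the protocol print ≤8.0%, so this may be an artefact of text extraction.

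**Conclusion.** The point holds in a limited form. For the secondary endpoints, the rule read with 4.4.2 and Table 2 cannot produce the promised LS means. That is algebra and needs no assumption. For HbA1c, the planned contrast omits the part of the difference carried by the baseline slope. It is removed in expectation when change is roughly linear in baseline, attenuated for a step measured with error or for a benefit that starts above 8.0%, and reversed in sign for one curved shape tried.

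A reader might go further and infer that the two HbA1c LS means come out almost equal whatever the truth, or that the table would show consistency even if nearly all benefit lay above 8.0%. Neither follows. Equality is in expectation and needs a near-linear relation; a step at 8.0% survives wholly or in part. With a standard error near 0.31, the observed gap exceeds 0.2 in about half of trials even when its expectation is zero. The supportable statement is that the table could suggest consistency that is not there.

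The sizes rest on assumptions absent from the documents: the baseline distribution, within-person SD, shape of the relation, visit correlations and complete data. The primary test is unaffected.

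**What to change.** Amend SAP 4.7.1 for the baseline-HbA1c subgroup only:

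1. **Secondary endpoints:** enter the HbA1c category once, as SUBGROUP, and drop it as a separate covariate.
2. **HbA1c:** do not use LS means at the common baseline to judge consistency. Report subgroup mean changes without the continuous covariate, or LS means at each subgroup's own mean baseline. State that grouping on the Visit 2 value brings in regression to the mean, about 0.2 at within-person SD 0.3. Add a sensitivity analysis grouped on the Visit 1 central-laboratory HbA1c, noting that it removes that gap only as far as the errors at the two visits are independent.
3. **Cut-point:** confirm that the SAP uses the protocol's ≤8.0% and >8.0%.

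Item 1 costs nothing. Item 2 is a trade-off: Visit 1 is not the baseline defined in protocol 9.3.1 and SAP 4.1, so it belongs in a sensitivity analysis and should not replace the prespecified grouping. Overall the change is a few sentences and one modified program, with no new data.
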